5.3 Safety

An overall summary of adverse events (AE) will be provided, including for each group the number and the percent of subjects with all AE, all serious AE, all related AE, and all AE by severity. In addition, all adverse events, serious, and non-serious adverse events will be summarized and tabulated by preferred term, both overall and by severity, by time period of onset, and by operative site

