6.3 Analysis population

Full Analysis Set (FAS): The set of subjects determined following the intent-totreat (ITT) principle refers to the data set constituted by all subjects who participate in the randomized study and receive the investigational product (implant) (i.e., ITT population defined in the protocol).

Per Protocol Set (PPS): Refers to the subgroup of treatment population who completes the trial and excluded the population that seriously violates the protocol (which means that study subjects violating the inclusion criteria or meeting exclusion criteria, loss to follow-up during the trial, cross enrollment, out-of-specification use of investigational products, out-of-window time, etc.).

Safety Set (SS): Set of all subjects who participate in the study and use the investigational products and undergo at least one safety evaluation after baseline. (The definitions of SS and FAS are the same. Therefore, SS is not defined separately).

Actual Treatment Set (ATS): All patients who participate in the randomized grouping, complete the trial, actually receive the scheduled treatment in the study (not necessarily consistent with the results of randomized grouping) and do not seriously violates the protocol. On the basis of PPS, only cross-enrolled patients are included, but they are then grouped and analyzed according to their actual treatment, i.e., the actual treatment set is formed.

The primary efficacy analysis will be based on FAS, PPS and ATS (if applicable). All baseline demographic data and secondary efficacy indicator analysis will be performed on the basis of FAS, and the safety evaluation will be performed on the basis of FAS.

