6.6 Significant level and statistical analysis software

For the primary endpoint, statistical analysis will be performed at the one-sided 0.025 significance level (corresponding to the one-sided confidence limit of the 95% confidence interval). For other endpoints, all statistical analysis will be performed at the two-sided 0.05 significance level (except for special instructions). SAS[®] 9.4 statistical software will be used for statistical analysis.

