7.7 Concomitant medication, adverse events (AEs) or serious adverse events

(SAEs)

For concomitant medication, the subject's concomitant medication is provided in the form of a list.

The AEs and investigational device-related AEs in subjects will be tabulated and summarized, respectively. The list of subjects reported with AEs/ investigational device-related AEs includes site number, random number, group, age, gender, name of AE (SOC code), name of AE (PT code), time of postoperative occurrence (day), remission time (day), severity, measures taken, outcome, correlation with surgery, correlation with investigational device, withdrawal from the trial due to AEs, whether it is unanticipated adverse device effect (UADE), device failure or SAE.

Investigational device-related AEs refer to those "definitely related", "probably related" and "possibly related" with the investigational device;

Time of postoperative occurrence (day) = Date of occurrence of AE - Date of surgery,

Remission time (day) = End date of AE - Date of occurrence of AE.

The summary form will list the total number of cases of AEs/investigational device-related AEs, the total number of subjects suffering from AEs/investigational device-related AEs.

Wherein, the total case of AEs refers to the number of subjects suffering from AEs, and the AEs occur in the subject at least one time, which is considered as "Yes";

Statistical analysis of the severity of adverse events, the relationship with the study device and the relationship with the surgery was performed. If multiple adverse events occurred in a patient, the analysis was performed with the most severe or highest correlation.

The SAEs and investigational device-related SAEs in subjects will be tabulated and summarized, respectively; such data will be presented in the same form as AEs. The list of subjects reported with SAEs/investigational device-related SAEs includes site number, random number, group, age, gender, name of SAE (SOC code), name of SAE (PT code), time of postoperative occurrence (day), remission time (day), severity, outcome, correlation with surgery, correlation with investigational device and SAE.

The list and summary of UADEs in subjects will be presented respectively in the same form as AEs.

The calculation method of the time of postoperative occurrence (day) and remission time (day), the presentation of the summary form and the statistical principle are the same as those for AEs.

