Site No.	Random No.	Group	Age	Gender	Name of AE (SOC code)	Name of AE (PT code)	Time of postoperative occurrence (day)	Remission time (day)	Severity	Measures taken	Outcome	Correlation with the surgery	Correlation with the investigational device	Withdrawal from the trial due to AEs	Whether it is UADE	Whether it is device failure	Whether it is SAE
XXX	XXX	XXX	XXX	XXX	XXX	XXX	XXX	XXX	XXX	XXX	XXX	XXX	XXX	XXX	XXX	XXX	XXX
XXX	XXX	XXX	XXX	XXX	XXX	XXX	XXX	XXX	XXX	XXX	XXX	XXX	XXX	XXX	XXX	XXX	XXX
XXX	XXX	XXX	XXX	XXX	XXX	XXX	XXX	XXX	XXX	XXX	XXX	XXX	XXX	XXX	XXX	XXX	XXX
																	

Table 79Specific description on subjects with AEs

Notes: 1. Time of postoperative occurrence (day) = Date of occurrence of AE - Date of surgery; Remission time (day) = End date of AE - Date of occurrence of AE.

Adverse event	S	tudy group	Contr	rol group
	Number of events	Number of subjects (N=XXX)	Number of events	Number of subjects (N=XXX)
Name of AE (SOC code)	XXX	XXX(XX.XX% [#])	XXX	XXX(XX.XX%)
Name of AE (PT code)	XXX	XXX(XX.XX%)	XXX	XXX(XX.XX%)
Name of AE (PT code)				
Name of AE (SOC code)	XXX	XXX(XX.XX%)	XXX	XXX(XX.XX%)
Name of AE (PT code)	XXX	XXX(XX.XX%)	XXX	XXX(XX.XX%)
Name of AE (PT code)				

Table 80Summary of AEs

Notes: 1. #: Percentage of AEs = Number of subjects suffering from AEs/Total number of subjects in the study group or the control group;

2. Investigational device: Trochanteric Fixation Nail Advanced (TFNA); control device: Proximal Femoral Nail Antirotation (PFNA-II);

145/129

Adverse event	Study group	Control group	Statistics	P value
Total number of AEs				
Number of subjects (N miss)	XXX (XXX)	XXX (XXX)	X.XXXX	X.XXXX
Yes	XXX (XX.X%)	XXX (XX.X%)		
No	XXX (XX.X%)	XXX (XX.X%)		
Event rate difference (study grow	up-control group) and	95%CI XX.X [2	XX.X; XX.X]	

Table 80Summary of AEs (continued 1)

Notes: 1. The total number of AEs refers to the number of subjects suffering from AEs, and the AEs occur in the subject at least one time, which is considered as "Yes".

2. The likelihood ratio Chi-square test or Fisher's exact probability test is used to analyze the intergroup comparison of qualitative indicators;

3. The difference of event rate and 95% confidence interval were analyzed by Wald test with continuous correction;

Table 81	Specific	description or	1 subjects v	with investigational	device-related AEs
		I I I I I I I I I I I I I I I I I I I	J		

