Site No.	Random No.	Group	Age	Gender	Name of AE (SOC code)	Name of AE (PT code)	Time of postoperative occurrence (day)	Remission time (day)	Severity	Measures taken	Outcome	Correlation with the surgery	Correlation with the investigational device	Withdrawal from the trial due to AEs	Whether it is UADE	Whether it is device failure	Whether it is SAE
XXX	XXX	XXX	XXX	XXX	XXX	XXX	XXX	XXX	XXX	XXX	XXX	XXX	XXX	XXX	XXX	XXX	XXX
XXX	XXX	XXX	XXX	XXX	XXX	XXX	XXX	XXX	XXX	XXX	XXX	XXX	XXX	XXX	XXX	XXX	XXX
XXX	XXX	XXX	XXX	XXX	XXX	XXX	XXX	XXX	XXX	XXX	XXX	XXX	XXX	XXX	XXX	XXX	XXX

Notes: 1. Time of postoperative occurrence (day) = Date of occurrence of AE - Date of surgery; Remission time (day) = End date of AE - Date of occurrence of AE.

Investigational device- related AE	St	udy group	Control group			
	Number of events	Number of subjects (N=XXX)	Number of events	Number of subjects (N=XXX)		
Name of AE (SOC code)	XXX	XXX(XX.XX% [#])	XXX	XXX(XX.XX%)		
Name of AE (PT code)	XXX	XXX(XX.XX%)	XXX	XXX(XX.XX%)		
Name of AE (PT code)						
Name of AE (SOC code)	XXX	XXX(XX.XX%)	XXX	XXX(XX.XX%)		
Name of AE (PT code)	XXX	XXX(XX.XX%)	XXX	XXX(XX.XX%)		
Name of AE (PT code)						

Table 82	Summary of investigational device-related AEs
----------	---

Notes: 1. #: Percentage of investigational device-related AEs = Number of subjects suffering from investigational device-related AEs/Total number of subjects in the study group or the control group;

2: Investigational device-related AEs refer to those "definitely related", "probably related" and "possibly related" with the investigational device;

Investigational device-related AE	Study group	Control group	Statistics	P value
Total number of investigational device-	related AEs			
Number of subjects (N miss)	XXX (XXX)	XXX (XXX)	X.XXXX	X.XXXX
Yes	XXX (XX.X%)	XXX (XX.X%)		
No	XXX (XX.X%)	XXX (XX.X%)		
Event rate difference (study group-contro	l group) and 95%CI	XX.X [XX.X;	XX.X]	

Table 82 Summary of investigational device-related AEs (continued)

Notes: 1. The total number of investigational device-related AEs refers to the number of subjects suffering

from investigational device-related AEs and the investigational device-related AEs occur in the subject at least one time, which is considered as "Yes".2: Investigational device-related AEs refer to those "definitely related", "probably related" and

2: Investigational device-related AEs refer to those "definitely related", "probably related" and "possibly related" with the investigational device;

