
3. The likelihood ratio Chi-square test or Fisher's exact probability test is used to analyze the intergroup comparison of qualitative indicators;

4. The difference of event rate and 95% confidence interval were analyzed by Wald test with continuous correction;

Indicator			control group	• (N=XXX ^{#1})) P
Total number of adverse even	ents				
	XXX ^{#2} ($XX.X^{3}$)	XXX ^{#2} (X	X.X ^{#3})	X.XXXX
Eve	nt difference (study	group-control g	group) and 95%C	XX.X [2	XX.X; XX.X]
Total number of device rela		XX.X ³)	XXX ^{#2} (X	X.X ^{#3})	X.XXXX
Event ra	te difference (stud	y group-control	group) and 95%C	CI XX.X [2	XX.X; XX.X]
Total number of surgery rela			XXX ^{#2} (X	X.X ^{#3})	X.XXXX
	te difference (study	• •	group) and 95%C	CI XX.X [2	XX.X; XX.X]
Notes: 1. Devices related related" or "defini 2. Surgery related a related" or "defin 3.#1: Total numbe #3: Total numb 4. Group t-test is us 5. Investigational d	adverse events are tely related" to the dverse events are the hitely related" to sur- er of subjects; #2: er of events/total missed to analyze Even	the adverse even study devices; he adverse even rgery; Total number of umber of patien at rate difference Fixation Nail A	ts that are "proba of events; ts: the average nu e (study group-co	bly related" or umber of events ontrol group) an	"possible s per subject; id 95%CI

Table 83 Summary of AEs (Number of events per subject)

Indicator	Study group control g	roup statistic	Р	
Severity				
NO. (Nmiss)	XXX (XXX)	XXX (XXX)	X.XXXX	X.XXXX
mild	XXX (XX.X%)	XXX (XX.X%	o)	
moderate	XXX (XX.X%)	XXX (XX.X%	%)	
severe	XXX (XX.X%)	XXX (XX.X	(%)	
Device related			,	
NO. (Nmiss)	XXX (XXX)	XXX (XXX)	X.XXXX	X.XXXX
Not related	XXX (XX.X	%) XXX (X	(X.X%)	
Unlikely related		%) XXX (X		
Possible related	XXX (XX.X%	$\dot{\mathbf{x}}$ \mathbf{x} \mathbf{x}	K.X%)	
probably related) XXX (XX		
definitely related	XXX (XX.X		· · ·	
Surgery related	×	, , , , , , , , , , , , , , , , , , , ,	,	
NO. (Nmiss)	XXX (XXX)	XXX (XXX)	X.XXXX	X.XXXX
Not related	XXX (XX.X%			
Unlikely related		%) XXX (X	(X.X%)	
possible related	XXX (XX.X%	$\dot{\mathbf{XXX}}$	X.X%)	
probably related) XXX (XX		
definitely related	XXX (XX.)		XX.X%)	

Table 84Statistical analysis results of the severity and the device related
AEs (According subject)

Notes: 1. If more than one adverse event occurred in a subject, the analysis was performed with the highest severity or correlation;

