2. The likelihood ratio Chi-square test or Fisher's exact probability test is used to analyze the intergroup comparison of qualitative indicators;

Indicator (N=XXX#1)	Study group (N=XXX#1)		=XXX#1) total
Severity			
mild	XXX#2 (XX.X%#3)	XXX (XX.X%)	XXX (XX.X%)
moderate	XXX (XX.X%)	XXX (XX.X%)	XXX (XX.X%)
severe	XXX (XX.X%)	XXX (XX.X%)	XXX (XX.X%)
Device related			
Not related	XXX (XX.X%)) XXX (XX.X%)	XXX (XX.X%)
Unlikely related	XXX (XX.X%)) XXX (XX.X%)	XXX (XX.X%)
Possible related	XXX (XX.X%)	XXX (XX.X%)	XXX (XX.X%)
probably related	XXX (XX.X%)	XXX (XX.X%)	XXX (XX.X%)
definitely related	XXX (XX.X%)	XXX (XX.X%)	XXX (XX.X%)
Surgery related			
Not related	XXX (XX.X%)	XXX (XX.X%)	XXX (XX.X%)
Unlikely related	XXX (XX.X%)	XXX (XX.X%)	XXX (XX.X%)
possible related	XXX (XX.X%)	XXX (XX.X%)	XXX (XX.X%)
probably related	XXX (XX.X%)	XXX (XX.X%)	XXX (XX.X%)
definitely related	XXX (XX.X%	b) XXX (XX.X%) XXX (XX.X%)

Table 85Statistical analysis results of the severity and the device related
AEs (Number of events per subject)

Notes: 1.#1: Total number of subjects; #2: Total number of events;

2.#3: Total number of events/total number of subjects: the average number of events per subject;
3. Investigational device: Trochanteric Fixation Nail Advanced (TFNA); control device: Proximal Femoral Nail Antirotation (PFNA-II)

						-	*	U					
Site No.	Random No.	Group	Age	Gender	Name of SAE (SOC code)	Name of SAE (PT code)	Time of postoperative occurrence (day)	Remission time (day)	Severity	Outcome	Correlation with the surgery	Correlation with the investigational device	SAE condition
XXX	XXX	XXX	XXX	vvv	XXX	XXX	XXX	XXX	XXX	XXX	XXX	XXX	XXX
ΛΛΛ	ΛΛΛ	ΛΛΛ	ΛΛΛ	XXX	ΛΛΛ	ΛΛΛ	ΛΛΛ	ΛΛΛ	ΛΛΛ	ΛΛΛ	ΛΛΛ	ΛΛΛ	ΛΛΛ
XXX	XXX	XXX	XXX	XXX	XXX	XXX	XXX	XXX	XXX	XXX	XXX	XXX	XXX
XXX	XXX	XXX	XXX	XXX	XXX	XXX	XXX	XXX	XXX	XXX	XXX	XXX	XXX

Table 86 Specific description on subjects with SAEs

Notes: 1. Time of postoperative occurrence (day) = Date of occurrence of SAE - Date of surgery; Remission time (day) = End date of SAE - Date of occurrence of SAE.

SAE	Sti	ıdy group	Con	Control group			
	Number of events	Number of subjects (N=XXX)	Number of events	Number of subjects (N=XXX)			
Name of SAE (SOC code)	XXX	XXX(XX.XX% [#])	XXX	XXX(XX.XX%)			
Name of SAE (PT code)	XXX	XXX(XX.XX%)	XXX	XXX(XX.XX%)			
Name of SAE (PT code)							
Name of SAE (SOC code)	XXX	XXX(XX.XX%)	XXX	XXX(XX.XX%)			
Name of SAE (PT code)	XXX	XXX(XX.XX%)	XXX	XXX(XX.XX%)			
Name of SAE (PT code)							

Table 87Summary of SAEs

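### Tables 84 and 91 test severity and relatedness only among subjects who had an event; no table compares severe or surgery-related events by subject on the whole FAS

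*SAP*

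**What the plan says.** **Protocol 5.3 (Safety)** asks for an overall AE summary giving, for each group, "the number and the percent of subjects with all AE, all serious AE, all related AE, and all AE by severity".

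**SAP 6.3** sets the population: "the safety evaluation will be performed on the basis of FAS". **SAP 6.6** sets the level: "For other endpoints, all statistical analysis will be performed at the two-sided 0.05 significance level".

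**SAP 7.7** gives the rule for subjects with several events: "If multiple adverse events occurred in a patient, the analysis was performed with the most severe or highest correlation". It names no category and no denominator for subjects with none.

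**Tables 84 and 91** repeat that rule in their notes: "If more than one adverse event occurred in a subject, the analysis was performed with the highest severity or correlation". Each has three blocks: severity (mild, moderate, severe), relation to device, and relation to surgery (both from not related to definitely related). Each block is headed by a number of subjects with a missing count. The notes give the test: "The likelihood ratio Chi-square test or Fisher's exact probability test is used to analyze the intergroup comparison of qualitative indicators".

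**Sibling tables** are built differently. Table 80 defines its percentage as "Percentage of AEs = Number of subjects suffering from AEs/Total number of subjects in the study group or the control group". Table 82 does the same for device-related AEs: "Number of subjects suffering from investigational device-related AEs/Total number of subjects in the study group or the control group". Tables 87 and 89 follow the pattern for SAEs. All four have a No row and a rate difference with 95% CI.

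**The concern.** A subject without an AE has no severity and no relatedness, so fits none of the rows in Table 84; the same holds in Table 91 for a subject without an SAE. The only place left in the shell is the missing count. Whatever denominator is used for the percentages, a test on the listed rows leaves these subjects out.

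What is then compared is the mix of severities among subjects who had an event, not the risk of a severe event between the randomized arms. The two can differ, because having an event is itself an outcome of treatment.

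At stake is the only subject-level severity comparison in a registration trial whose secondary endpoints include the comparison of adverse events.

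**Working it through.** **Which comparisons exist on all subjects**

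| Question | All-subject table | Unit |
|---|---|---|
| Any AE / any SAE | 80 / 87 | subjects, difference and CI |
| Device-related AE / SAE | 82 / 89 | subjects, difference and CI |
| Surgery-related AE / SAE | 83 / 90 | events per subject, difference and CI |
| Events by severity and by relation | 85 / 92 | events per subject, no test |
| Subjects with a severe event | none | – |
| Subjects with a surgery-related event | none | – |

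**Group size.** SAP 6.2 assumes 95% union in both arms, a 0.10 margin and 80% power; SAP 6.6 gives one-sided 0.025. Then n = (1.960 + 0.842)² × 2 × 0.95 × 0.05 / 0.10² = 74.6, so 75. With 20% attrition, 75/0.80 = 93.75, so 94. The plan's 75 and 94 are reproduced. I use 94 per arm only to fix the size of the example.

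**AE rates.** The documents give none by severity, so the counts below are assumptions.

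**Example: only severe events doubled.** Subjects by worst severity (mild/moderate/severe): TFNA 16/12/24, PFNA-II 16/12/12. Subjects with any AE: 52 and 40. The test statistic is G = 2 Σ O ln(O/E).

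1. Table 84 layout (three rows, 92 subjects). Expected TFNA counts: 32 × 52/92 = 18.09, 24 × 52/92 = 13.57, 36 × 52/92 = 20.35. G = 2.51 on 2 df, **P = 0.29**. The smallest expected count is 10.4.
2. Table 80, any AE: 52/94 = 55.3% v 40/94 = 42.6%. G = 3.07 on 1 df, **P = 0.080**; continuity-corrected Wald 95% CI −2.5 to 28.0 points.
3. Table 84 with a no-AE row added (42 v 54): G = 5.58 on 3 df, **P = 0.13**.
4. Severe yes/no on all subjects: 24/94 = 25.5% v 12/94 = 12.8%. G = 5.03 on 1 df, **P = 0.025** (Fisher P = 0.04). Difference 0.1277; SE = √(0.2553 × 0.7447/94 + 0.1277 × 0.8723/94) = 0.0566; half-width 1.96 × 0.0566 + 1/94 = 0.1216. The 95% CI is **0.6 to 24.9 points**.

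**Why both planned tests miss it.** The risk ratio for severe events is the risk ratio for any AE times the ratio of severe shares among subjects with an AE: (52/40) × [(24/52)/(12/40)] = 1.30 × 1.54 = 2.0. Table 80 sees the first factor and Table 84 the second; neither sees the product.

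**Simulation, 3,000 trials per setting, 94 per arm.** Entries are the percent of trials with likelihood-ratio P < 0.05. Severe risk is 20% v 10% in both settings, and 10% of control subjects have each severity as their worst.

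| Setting | Table 84 | Table 80 | Table 84 + no-AE row | Severe yes/no, all subjects |
|---|---|---|---|---|
| Only severe doubled | 22 | 31 | 36 | 49 |
| Every severity doubled | 5 | 99 | 96 | 47 |

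**The case against.** **The excess is often visible elsewhere.** A reader might infer that Table 84 hides any doubling of severe risk. Take 60 TFNA subjects with an AE, 12 of them severe, against 30 and 6. Among subjects with an AE, severe events are 20% v 20% (P = 1.0), while the risk is 12/94 = 12.8% v 6/94 = 6.4%. But Table 80 would show 60/94 v 30/94, a difference of 31.9 points (95% CI 17.3 to 46.5, Fisher P = 0.00002), and Table 84 would print the counts 12 and 6. The all-subject severe comparison is not significant here either (Fisher P = 0.21, 95% CI −3.0 to 15.8 points). So this case shows an uninformative test, not a lost signal. The objection stands for excesses that run across all severities.

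**False alarms are not shown.** A reader might also infer that the layout invents differences. With 6 severe in each arm, 6/60 = 10% v 6/30 = 20% looks uneven, but Fisher P = 0.20.

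**The percentage denominator is open.** It is tempting to say that Table 84 will print percentages of subjects with an event. The SAP does not say so, and the sibling tables divide by all subjects. If that applies here, the percentages would be right. The test on the listed rows would still omit event-free subjects.

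**Related data are planned.** Tables 83, 85, 90 and 92 give events per subject, and the listings in Tables 79 and 86 give severity and relation to surgery for each event. That narrows the gap. It does not close it, because one subject with several events can drive an event count.

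**Little hangs on it formally.** SAP 7.4 treats adverse events as largely descriptive, no decision rule uses these tables, and Protocol 5.3 asks for numbers and percents, not a severity test. That is right. But the SAP does plan a test, and as laid out it is not a comparison of risk between arms.

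**Conclusion.** The point holds in a limited form. The test in Tables 84 and 91 is confined to subjects with an event, and no planned table compares the proportion of all FAS subjects with a severe event or with a surgery-related event. The documents do not support saying that a severe excess would generally be hidden, or that a false one would be created.

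The exposed case is an excess confined to severe events. In the example above, neither planned subject-level P value falls below 0.05, while the direct comparison gives 25.5% v 12.8% with a CI that excludes zero. That result rests on assumed counts with severe AEs in 13% to 26% of subjects. At lower rates even the direct comparison may be inconclusive: 8/94 v 4/94 gives likelihood-ratio P = 0.23. Its estimate and interval would still describe the right quantity.

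This should be corrected before the tables are run. It does not touch the primary endpoint.

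**What to change.** In Tables 84 and 91:

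- State that percentages use all FAS subjects of the arm.
- Add a no-AE row (Table 84) or a no-SAE row (Table 91) to the severity, device and surgery blocks.
- Add yes/no lines for any severe event and any surgery-related event on all FAS subjects, with rate difference and 95% CI by the method already used in Tables 80, 82, 87 and 89.

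The yes/no lines matter most, since the extra row alone gives P = 0.13 in the example. Add one sentence to SAP 7.7 on how subjects without an event are classified. The cost is two table shells and a few lines of programming; the data are already collected.
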